3.2 Sensitivity Analysis

- Re-run analysis using dominant/recessive genetic models

4. Outcome Measures

- Primary endpoint: CMVO
- Secondary endpoints:
 - In-hospital mortality

- Left Ventricle Ejection Fraction
- Ventricular fibrillation
- N-terminal Pro-brain Natriuretic Peptide
- Six-minute Walk Test

5. Statistical Software

- R

6. Sample Size Justification

- 80 patients (40 CMVO+/40 CMVO-) provides:
 - 80% power to detect $OR \geq 4.0$ ($\alpha=0.05$, two-tailed)
 - Assumes SNP prevalence = 12–69% (average 50%)

7. Data Presentation

- Tables:
 - Baseline characteristics (Me [Q1; Q3] for continuous; n (%) for categorical)
 - SNP frequencies by group
 - Multivariate ORs for CMVO predictors
- Figures:
 - Flowchart of patient inclusion
 - Forest plot of significant SNPs

8. Ethical Considerations

- All analyses will use anonymized data (patient serial numbers only).
- Protocol deviations documented in CONSORT flowchart.
- Approval:

Local Ethics Committee Protocol Version: 1.0

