Identifying genetic determinants of CMVO holds significant scientific novelty and could form the basis for a novel diagnostic system to predict this complication. Such a system would be clinically valuable, reducing PCI-related risks and improving patient outcomes.

Study Objective: to identify genetic determinants of coronary microvascular obstruction development during percutaneous coronary interventions.

Study Design

A matched case-control study will be conducted to examine the role of specific single nucleotide polymorphisms (SNPs) as predictors of coronary microvascular obstruction (CMVO) development. The study will enroll 80 patients meeting the inclusion/exclusion criteria who have provided written informed consent. Patients will be allocated into two groups in a 1:1 ratio:

- Group 1 (CMVO+): 40 patients with myocardial infarction (MI) who developed CMVO following PCI
- Group 2 (CMVO-, control group): 40 patients with MI who did not develop CMVO following PCI

Group allocation will be performed by the principal investigator. The groups will be matched by sex and age using the "matched pairs" method [9]. For each patient in the CMVO+ group, a corresponding patient of the same sex and similar age (± 5 years) will be selected from the pool of MI patients who underwent PCI without CMVO development.

The required sample size (80 patients) was determined based on the following parameters: alpha error level – 5 %, study power – 80 %, group ratio – 1:1, minimum detectable odds ratio – 4.0, expected prevalence of the studied SNPs in the population: 12–69 % (average 50%) [10]. Among the 40 planned matched pairs, 20 pairs must be discordant (i.e., the paired patients must differ in the presence or absence of the predictor).

The study will be conducted in several stages:

1. Patient Screening

- The principal investigator will assess inclusion/exclusion criteria.
- Determine eligibility for study group allocation.
- Performed in the catheterization laboratory immediately after PCI completion.

2. Informed Consent Process

- Eligible patients will provide written informed consent for genetic testing.

- Patients will be assigned to respective study groups.
- Conducted in the catheterization laboratory.

3. Biological Sample Collection

- Blood sampling for genetic analysis.
- Performed in the catheterization laboratory.

4. Sample Processing and Transportation

- Blood sample processing.

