Appendix B

SNPs Planned for Investigation

Gene	SNP	Identifier	Possible genotypes and their proportion in the population (reference and alternative)
ADD1 – α -adductin	1378 G>T (Gly460Trp)	rs4961	G=0.806737; T=0.193263
AGT – angiotensinogen	704 T>C (Met235Th)	rs699	A=0.545132; G=0.454868
	521 C>T (Thr174Met)	rs4762	G=0.878133; A=0.121867
AGTR1 – angiotensin II receptor type 1	1166 A>C	rs5186	A=0.721723; C=0.278277
AGTR2 – angiotensin II receptor type 2	1675 G>A	rs1403543	G=0.478265; A=0.521735
CYP11B2 – cytochrome 11b2 – aldosterone synthase	-344 C>T	rs1799998	A=0.573264; G=0.426736
GNB3 – beta 3 subunit of G protein – guanine-binding protein	825 C>T	rs5443	C=0.668330; T=0.331670
eNOS – nitric oxide synthase	-786 T>C	rs2070744	C=0.34927; T=0.65073
	894 G>T (Glu298Asp)	rs1799983	T=0.31468; G=0.68532
EDN1 – endothelin 1	594 G>T (Lys198Asn)	rs5370	G=0.780864; T=0.219136
F2 – prothrombin	20210 G>A	rs1799963	G=0.98867; A=0.01133

Gene	SNP	Identifier	Possible genotypes and their proportion in the population (reference and alternative)
F5 – proaccelerin	1691 G>A (Arg506Gln)	rs6025	G=0.951; A=0.049
F7 – proconvertin	10976 G>A (Arg353Gln)	rs6046	G=0.882035; A=0.117965
F13 – fibrinase	103 G>T (Val34Leu)	rs5985	G=0.786; T=0.214
FGB – fibrinogen	-455 G>A	rs1800790	G=0.81485; A=0.18515
ITGA2- α 2 – integrin	807 C>T (Phe224Phe)	rs1126643	C=0.610691; T=0.389309
ITGB3- β 3 – integrin	1565 T>C (Leu33Pro)	rs5918	T=0.851958; C=0.148042
SERPINE1 (PAI-1) – serpin	-675 5G>4G	rs1799762	4G=0.48510; 5G=0.51490
MTHFR – methylenetetrahydrofolate reductase	677 C>T (Ala222Val)	rs1801133	G=0.659842; A=0.340158
	1298 A>C (Glu429Ala)	rs1801131	T=0.695830; G=0.304170
MTR – B12 dependent methionine synthase	2756 A>G (Asp919Glu)	rs1805087	A=0.808600; G=0.191400
MTRR – methionine synthase reductase	66 A>G (Ile22Met)	rs1801394	A=0.482820; G=0.517180

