2.1 Data Collection

- Genetic data: SNP genotypes (binary: variant present/absent)
- Clinical data:
 - demographics
 - angiographic parameters
 - laboratory values
 - procedural details
 - hospitalization outcomes
 - CMVO presence/absence

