3.1 Statistical Analysis

- Univariate analysis:
 - McNemar's test (matched case-control design) for categorical SNPs
 - Odds ratios (OR) with 95% confidence intervals
- Multivariate analysis:
 - Conditional logistic regression
 - OR with 95% confidence intervals

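### The 80% power for OR ≥ 4.0 is stated for SNP prevalence 12–69%, but 40 pairs give it only for about 18–53%, and only with uncorrected McNemar

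*SAP*

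**What the plan says.** SAP section 6 attaches 80% power for an odds ratio of 4.0 or more (alpha 0.05, two-tailed) to 40 CMVO+ and 40 CMVO- patients, and gives the exposure assumption as "Assumes SNP prevalence = 12–69% (average 50". The sample-size paragraph under Study Design in the protocol uses the same inputs, with "expected prevalence of the studied SNPs in the population: 12–69 % (average 50", and adds: "Among the 40 planned matched pairs, 20 pairs must be discordant". Neither document says that the 80% applies only at the average, and neither gives power at any other prevalence.

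Three other places bear on the figure:

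- SAP section 2.1 defines the exposure as "SNP genotypes (binary: variant present/absent".
- SAP section 3.1 names the test as "McNemar's test (matched case-control design) for categorical SNPs", without saying whether it is uncorrected, continuity-corrected or exact.
- The protocol's Appendix B lists 22 SNPs with population allele proportions. They include F2 at "G=0.98867; A=0.01133" and F5 with an A allele at 0.049.

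**The concern.** In a matched design, power depends on the number of discordant pairs. At a fixed odds ratio that number depends on exposure prevalence: it peaks near 33% and falls away on both sides. A calculation done at a 50% average therefore cannot be carried over to a range of 12–69% without checking the ends.

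The primary objective is SNP-by-SNP association, so one power figure has to serve 22 separate tests. SAP section 3.1 does plan odds ratios with 95% confidence intervals, and these would show imprecision. But the displays listed in SAP section 7 are "SNP frequencies by group", multivariate odds ratios, and "Forest plot of significant SNPs". No display is named that would show the univariate interval for a non-significant SNP. For such a SNP, the stated 80% may be the only indication of precision a reader has.

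**Working it through.** **Inputs.** 40 pairs, OR 4.0, two-sided alpha 0.05, target power 80% (protocol Study Design; SAP section 6). Exposure is taken as independent within pairs and each SNP is tested at 0.05. With p the exposure prevalence in controls:

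- prevalence in cases: p1 = 4p/(1+3p)
- probability that a pair is discordant: pd = p(1−p1) + p1(1−p) = 5p(1−p)/(1+3p)
- share of discordant pairs in which the case is the exposed member: 4/(1+4) = 0.8

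**Reproducing the plan's figure.** Discordant pairs needed = (1.96×0.5 + 0.8416×√(0.8×0.2))² / 0.3² = 19.3, rounded up to 20. At p = 0.50, p1 = 0.80 and pd = 0.50, so 40 pairs are expected to give 20 discordant pairs. The protocol's figures are reproduced.

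**Power across the stated range.** Power is the sum, over the possible numbers n of discordant pairs, of Bin(n; 40, pd) times the probability of rejection given n, with the split within n following Bin(n, 0.8).

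| Control prevalence | Expected discordant pairs | Uncorrected | Exact | Continuity-corrected | Pairs for 80% (uncorrected / exact) | OR detectable at 80% (uncorrected / exact) |
|---|---|---|---|---|---|---|
| 12% | 15.5 | 69% | 60% | 58% | 50 / 59 | 4.7 / 5.2 |
| 50% | 20.0 | 82% | 74% | 73% | 39 / 46 | 3.9 / 4.5 |
| 69% | 13.9 | 63% | 54% | 52% | 56 / 66 | 6.1 / 7.8 |

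Uncorrected power is at least 80% for p from 0.183 to 0.527, with a maximum of 85.9% near 33%. The maxima for the exact and continuity-corrected versions are 79.1% and 78.4%, so neither reaches 80% at any prevalence.

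**Power by SNP on the SAP's coding.** Carrier prevalence is 1−(1−q)² under Hardy-Weinberg. Here q is the Appendix B proportion of the variant allele, read from the SNP name, and all SNPs are treated as autosomal. With the uncorrected test:

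- *At least 80%:* 10 SNPs.
- *71–80%:* ITGA2 71%, eNOS -786 76%, MTHFR 677 77%, GNB3 78%, eNOS 894 79.8%.
- *Below 70% (exact test in brackets):* CYP11B2 66% (57%) if G is the variant allele or 41% (30%) if T is; F5 61% (52%); AGT 704 61% (52%); PAI-1 56% (46%); MTRR 51% (40%); AGTR2 50% (39%); F2 21% (6%).

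Twelve of 22 therefore miss 80%: ten because carrier prevalence is above about 53%, plus F2 and F5. The counts are the same under either reading of CYP11B2.

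F2 and F5 are below 12% both as alleles (1.1% and 4.9%) and as carriers (2.3% and 9.6%). For F2, 4.1 discordant pairs are expected at OR 4. An exact two-sided test needs at least 6, since 2×0.5⁵ = 0.063 and 2×0.5⁶ = 0.031.

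**Where the range and the average may come from.** This is inference, because neither document gives the derivation. Without F2 and F5, the second-listed alleles in Appendix B run from 0.118 (F7) to 0.685 (eNOS 894), which matches 12–69%, but their mean is 34%. The mean carrier prevalence without F2 and F5 is 50.1%, which matches the average, but carriers then range from 22% (F7) to 77% (AGTR2). The range and the average appear to sit on different scales.

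**The case against.** The strongest reply is that there is no error at the design point. Both documents give the 50% average, and 20 discordant pairs of 40 is what 50% yields, so the range could be read as loose background to a correct calculation. The arithmetic at 50% is indeed right, and the sample size itself is not faulted. But the range is what both documents state as the assumption, and nothing confines the 80% to its average.

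The second reply concerns scale. If 12% is an allele proportion, it corresponds to about 23% carriers and power of about 83%. On the carrier scale no SNP lies close to 12%: F5 is at 9.6% and the next is F7 at 22%. This is correct, and it removes the shortfall at the low end for every SNP except F2 and F5. It makes the high end worse, however, where AGTR2 and MTRR fall to about 50%. The statement fails on either scale.

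Third, the count of 12 belongs to carrier coding. Under the recessive model, which SAP section 3.2 plans as a sensitivity analysis, AGTR2, MTRR, PAI-1 and AGT 704 would have 82–85% power at OR 4. That is fair, but the main coding is variant present/absent. A mid-p McNemar test would give 80.0% at 50% and 80% or more for about 20–50%, so it does not rescue the ends of the range either.

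Finally, the planned confidence intervals limit the harm if they are reported for every SNP, and eNOS 894 misses by only 0.2 points. Both points stand. They bear on how serious the matter is, not on whether the power statement is right.

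**Conclusion.** The concern holds. The stated 80% is correct at 50% prevalence with uncorrected McNemar. It is wrong for the 12–69% range it is attached to: power is 69% and 63% at the two ends, and about 18–53% is the range actually covered. With the exact or continuity-corrected test it is not reached anywhere.

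The figures at 12%, 50% and 69% rest only on the plan's own inputs and on exposure being independent within pairs. The per-SNP figures also assume Hardy-Weinberg proportions, autosomal inheritance and the variant allele implied by each SNP name. The account of where 12–69% and 50% came from is inference, and the conclusion does not depend on it. This should be corrected before results are interpreted, but it does not undermine the design.

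**What to change.** Keep the 80 patients and all planned SNPs, and make these wording changes:

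- **SAP section 3.1:** name the McNemar version.
- **SAP section 6 and the protocol's sample-size paragraph:** restate the power on the carrier scale, for example: *With 40 pairs, a true OR of 4.0, two-sided alpha 0.05, exposure independent within pairs and the uncorrected McNemar test, power is 82% at 50% carrier prevalence, at least 80% for about 18–53%, 69% at 12% and 63% at 69%.* Adding the panel's own carrier limits without F2 and F5 (83% power at 22%, 50% at 77%) would tie this to the SNPs tested.
- **If the exact test is chosen:** give 74%, 60% and 54% at 50%, 12% and 69%, and say that 80% is not reached at any prevalence.
- **Limits of the claim:** state that F2 and F5 lie outside the assumed range, and that the 80% does not apply to them or to SNPs with carrier prevalence above about 53%.
- **Discordant pairs:** the sentence can stand as a planning number. If reworded: *About 20 discordant pairs are needed; at a true OR of 4 with independent exposures, at least 20 of 40 are expected when carrier prevalence is 20–50%.*

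A per-SNP table of carrier prevalence and power is optional. The cost is text in three places and a less favourable power statement. Recruitment and the set of SNPs tested do not change.
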